2.1. Background and Rationale

The IntelliVue Patient Monitors MP/MX series (with the etCO₂ module) is an FDA-approved device made by PHILIPS MEDIZINSYSTEME BOEBLINGEN GMBH (FDA 510(k) clearance K161531). It is commonly used in U.S. hospital and serves as the gold standard for the measurement of heart rate (HR) derived from an ECG signal and for the respiratory rate (RR) derived from etCO₂ density. However, it requires attachment to the patient's body, and cable connection to a display unit.

The RHEA Vital Sign Vigilance System was developed by Shenzhen Fiber Medical Technology Co. Ltd. It is designed for automatic, continuous and contact-less measurement of heart rate and respiratory rate of patients in a hospital or clinic setting. The system uses a sensor placed under the patient's mattress, and does not require a sensor to be fixed to the body. This provides a more comfortable solution for long-term continuous patient monitoring. Continuous monitoring of people's vital signs, in particular heart rate (HR) and respiratory rate (RR), may provide a mechanism to alert doctors or nurses of disease deterioration or an imminent severe clinical event. Monitoring people's vital signs outside an ICU often relies on nursing staff conducting checks at set intervals. The device can reduce the workload for nursing staff in non-ICU wards. The FDA-cleared EarlySense System 2.0 (K131379) developed by EarlySense Ltd. is also a contact-less system designed for continuous monitoring heart rate and respiratory rate of patients. It has been sold in over 20 U.S. hospitals since 2013. No recalls and adverse events have been reported. According to publicly available clinical results, the EarlySense System has shown an 86% reduction in Code Blue events, and a 45% reduction in Length of Stay (LoS) in the ICU for patients coming from the medical/surgical unit (1, 2). The EarlySense device applies the piezoelectric sensor while in comparison, the RHEA investigational device applies the optical fiber sensor. This difference leads to the RHEA device having a higher accuracy, capacity for greater patient weight range, longer sensor life and a lower cost. A Pilot Study on 25 healthy volunteers (20 adults and 5 children) showed that the RHEA device can obtain accuracy of overall mean root mean square difference (RMSD) of both HR and RR of 1.9 with the same testing procedure described in this current protocol (3). When comparing with the reference device- the EarlySense device on 9 adults, the RHEA device obtained results with no significant difference (pair t test is used to evaluate the results according to this protocol.)

Heart beat or respiratory movement produces a slight vibration which cannot be observed visually. However, the fiber sensor contained in the RHEA sensor unit will be deformed by the vibration, resulting in a change in the optical signal being transmitted. This changed optical signal is received by the bedside unit and converted into an electrical signal. The HR and RR then can be calculated by the bedside and displayed in real-time. The change in the optical signal can also be used to determine if the patient has exited the bed with a notification displayed on the bedside unit.

The system is intended for use as a 'contact-free' under-mattress device monitoring heart rate

and respiratory rate during sleep or resting condition, and to notify users when the patient exits the bed. The data can be displayed, exported and reviewed.

This protocol aims at verifying the safety and effectiveness of the investigational device in a general-care clinical environment.

2.2. Study Objectives

This clinical trial aims to verify that the RHEA Vital Sign Vigilance System can fulfill its intended use and meet its declared performance and functional specifications. Statistical analysis comparing the performance of the RHEA Vital Sign Vigilance System and the reference device EarlySense System 2.0 to the MP/MX series separately aims to demonstrate that the investigational device is substantially equivalent to the cleared reference device-EarlySense System 2.0 in safety and effectiveness.

3. Study Design

This will be a cross-over, ‘self-controlled’ study comparing the investigational device RHEA Vital Sign Vigilance System to an approved under-mattress device, EarlySense System (Model 2.0) (K131379). Both will be compared to the ‘gold standard’ Philips MP/MX series model Patient Monitor. The same Monitor Device must be used across all hospital wards in this study.

The testing will be conducted in three periods. In the Accuracy Tests (periods 1 and 2), one of the contact-free devices will be used to monitor the HR and RR, while being compared with the MP/MX series Patient Monitor. The RHEA investigational device and reference device will be used to monitor the same subject at different times (cross-over design), as the sensors of the two devices are placed at a similar location of the bed. HR and RR will be recorded for all three devices. Comparison of the performance of the two contact-free devices will be performed on the recorded results via statistical analysis. The third test will assess the ability of the RHEA device to accurately detect motion on or exit from the bed, as compared to the manual observation.

Three clinical trial sites will be selected in the U.S. A total of 77 adult subjects will be enrolled to complete 73 subjects (5% drop-out rate anticipated). Please see Section 10 for Sample Size justification. A site may enroll no more than half the total number of subjects for the study; i.e., up to 39 total subjects per site. It is anticipated that 33 days are needed for 77 recruited patients in total.

The testing duration for each subject will be one to two hours, including device placement, measurements, and device removal.

This is a multi-center study to be conducted in three hospitals. Wards in each site should be representative of non-ICU wards in U.S. hospitals (e.g., medical/surgical, oncology, orthopedics, long term acute care).

4. Subject Selection

Subjects will be hospitalized patients in general care non-ICU settings, who fulfill the following inclusion and exclusion criteria.

4.1. Inclusion Criteria

Subjects will be included if they meet the following inclusion criteria:

1. Male or female, 18 years old and above.
2. Provide written informed consent.
3. Weight ranging from 20 to 150 kg inclusive.
4. Are located in a non-ICU hospital setting.
5. Agree to not eat during the testing period.
6. Agree to keep still.

4.2. Exclusion Criteria

Subjects will be excluded if they have any of the following inclusion criteria:

1. Are connected to a device which may interfere with the device monitoring in this study.
2. Are receiving any bedside care which may be incompatible with the study procedures.
3. Sleep apnea.
4. Pregnant or breast feeding.
5. A likely need to receive or undergo a procedure during the testing period.
6. Cannot accept a nasal cannula, or have a monitor lead placed on the chest.
7. A significant medical condition in the judgement of the investigator, which may compromise the study testing procedures.
8. Are wearing pacemaker or defibrillator.

5. Investigational Device and Reference Device

The RHEA Vital Sign Vigilance System EL30 developed by Shenzhen Fiber Medical Technology Co. Ltd are designed for continuous and contact-less measurement of heart rate and respiratory rate. The system will also notify users when the patient exits the bed. The following devices will be used in this study.

Table 1: Study Devices

	Product name	Model	Manufacture	Clearance number
Investigational device	RHEA Vital Sign Vigilance System	EL30	Shenzhen Fiber Medical Technology Co. Ltd.	N/A

Reference device	EarlySense System	Model 2.0	EarlySense Ltd	K131379
Gold Standard device	IntelliVue Patient Monitors	MP/MX Series	PHILIPS MEDIZINSYSTEME BOEBLINGEN GMBH	K161531

5.1. Investigational Device Information

The RHEA Vital Sign Vigilance System is designed for continuous and contact-less measurement of heart rate and respiratory rate. The system will also notify users when the patient exits the bed. The system is intended for continuous measurement of respiration rate and heart rate for adults ($\leq 150\text{kg}$), in an automatic contact-less manner, in a hospital or clinic setting during sleep or resting condition.

The setup includes placing a sensor under the mattress, and a bedside unit on a nearby flat surface that can be viewed by the investigator.

5.2. Design Principle and Characteristics

Heart beat or respiratory movement produces a slight vibration which cannot be observed by the eyes. However, the fiber sensor contained in the sensor unit will be deformed by the vibration, resulting in a change in the optical signal being transmitted. This changed optical signal is received by the bedside unit and converted into an electrical signal. The heart rate and respiratory rate then can be calculated by the bedside and displayed in real-time. The change in the optical signal can also be used to determine if the patient has exited bed and a notification will be displayed on the bedside unit. The system does not require a sensor to be fixed to the patient body. This provides a more comfortable solution for long-term patient monitoring and solve the cable problems.

5.3. Device Components

The system incorporates the following three components:

- The bedside unit with battery [35 mm(Height) \times 241mm (Width) \times 600mm (Length)]
- The sensor unit [30mm (Height) \times 165mm (Width) \times 261mm (Length)]
- Proprietary exporting data software

5.4. Operation Training

Investigators will be trained on the device prior to beginning the study. The training will include: basic information regarding the investigational device, device preparation, operational instructions, device considerations, possible faults and their solutions, test contents, basic requirements and procedures, and records related to the control of the test.

6. Study Procedures

6.1. Screening

Patients will be screened to assess eligibility per the inclusion and exclusion criteria. Patients must provide written informed consent before being enrolled in the study.

Review of the eligibility criteria checklist will be recorded on the Case Report Form (CRF).

6.2. Baseline

The following information will be recorded prior to beginning the testing procedures:

- Gender, age.
- Height and weight.
- Location (ward/unit) where the subject is located.
- Clinical diagnosis (primary, and secondary if applicable)

6.3. Testing Procedures

The test will be conducted in three parts:

- Reference Device accuracy test
- Investigational Device accuracy test
- Motion and bed exit test

The following terms are used in the testing procedures below:

- Investigational Device (RHEA device)
- Reference Device (EarlySense device)
- Monitor Device (Gold Standard MP/MX series device)

Reference Device Accuracy Test

1. Two testers (Reference Device tester and Monitor Device tester) will record the following subject information in the CRF: subject ID, gender, height, weight, primary clinical diagnosis, time, site location (hospital and ward).
2. Place the Reference Device sensor unit under the mattress and beneath the chest of the subject according to the instructions for use. Place the bedside unit on a flat surface.
3. Synchronize the date and time of the Reference Device and the Monitor Device (to be equivalent).
4. Place the main units of the Reference Device and the Monitor Device in different locations in the subject's room such that they can only be viewed by their respective testers.
5. After the subject lies down on the bed, place the Monitor Device lead on the subject's chest

in accordance with the operational instruction of the Monitor Device.

6. Connect the etCO₂ module to the Monitor Device and apply the nasal cannula to the subject.
7. Turn on the Monitor Device and the Reference Device. Set the Monitor Device to “real-time monitoring mode”.
8. Instruct the subject to remain motionless. At one-minute intervals, the two testers will simultaneously record the heart rate (HR), respiratory rate (RR) and the current time using their respective device.
9. If the HR or RR value does not appear, or turns blurred on the screen (in this state only the last value is displayed rather than the current value), the Reference Device tester will mark it on the CRF.
10. Stop the test once 20 valid pairs of data are recorded for each subject. If certain values are marked (per Step 9 above), the data at that recorded point will not be considered in the analysis. More than 20 pairs will be collected in order to ensure that there are at least 20 valid pairs.

Investigational Device Accuracy Test:

1. Two testers (Investigational Device tester and the Monitor Device tester) will record the following subject information in the CRF: subject ID No., gender, height, weight, primary clinical diagnosis, time, site location (hospital and ward).
2. Place the Investigational Device sensor unit under the mattress and beneath the chest of the subject. Place the bedside unit on a flat surface or hang on the wall using the bracket.
3. Calibrate the device in accordance with the operator’s manual.
4. Synchronize the date and time of the Investigational Device and Monitor Device (to be equivalent).
5. Place the main units of the Investigational Device and the Monitor in different locations in the subject’s room such that they can only be viewed by their respective testers.
6. After the subject lies down on the bed, place the Monitor Device lead on the subject’s chest in accordance with the operational instruction of the MP/MX series Patient Monitor.
7. Connect the etCO₂ module to the Monitor device and apply the nasal cannula to the subject.
8. Turn on the Monitor Device and the Investigational Device. Set the Monitor Device to “real-time monitoring mode”.
9. Instruct the subject to remain motionless. At one-minute intervals, the two testers will simultaneously record the HR, RR and the current time using their respective device.
10. If HR or RR value does not appear or turns darker and with a mark “?” after the value on the screen (in this state only the last value is displayed rather than the current value), the Investigational Device tester will mark it on the CRF.

11. Stop the test once 20 valid pairs of data are recorded for each subject. If certain values are marked (per Step 10 above), the data at that recorded point will not be considered in the analysis. More than 20 pairs will be collected in order to ensure that there are at least 20 valid pairs.

Motion and Bed Exit Test:

This test will be conducted only on subjects who can move and exit the bed easily.

The Monitor Device tester will ask the subject to turn or move ten times and exit the bed for three times randomly in five minutes. The Monitor Device tester will record the time of these events on the CRF. At the same time, the Investigational Device tester will observe if there is an “unexpected motion” or “bed exit” notification on the screen of the Investigational Device and will record the time of this event on the CRF.

Device Testing Considerations:

1. At the baseline for each subject, make sure the following information is recorded: subject ID, date of birth, gender, height, weight, location, time and clinical diagnosis. Adverse events should be recorded and kept during the tests. The record should be signed by the testers.
2. It is important that nothing be allowed to shake the bed during the test. Anything that will produce vibration (such as a phone or another person) is not allowed to be on the bed during the test.
3. Make sure there is sufficient stable time before the HR and RR results are recorded for the Investigational Device and Reference Device. Thirty seconds is considered to be reasonable for Investigational Device and 1 min for Reference Device. That is to say, if the subject has to turn, stand up or move during the test, record data 30 seconds after the subject lies down and keeps still again. One minute should be left between two record groups for the independence of the data. If the subject moves or is out of the bed, record data 30 seconds after the subject lies down and keeps still again.

7. Device Safety and Stability Evaluation

Safety and stability data should be recorded in the CRF for Investigational device only.

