10.2. Primary Variables

The primary variables for the analysis of heart rate (HR) and respiratory rate (RR) are each the overall mean root mean square difference (RMSD), defined as the mean of the individual subject RMSDs. For each subject, the RMSD is calculated as:

$$\text{RMSD} = \text{sqrt}\{ \sum (Y_R - Y_G)^2 / n \}$$

where Y_R and Y_G are the paired values for the RHEA Vital Sign Vigilance System and the gold standard method (Patient Monitor), respectively, and n is the number of data pairs. If motion or a bed exit occurs within 20 seconds preceding the recording period for a given data pair, the data pair at that time point will not be used in the analysis. A total of 20 pairs of measurements are

planned for each subject. If more than 20 measurements are collected for a subject, then only the first 20 will be used. If fewer than 20 measurements are collected for a subject for any reason, that subject will still be included in the analyses.

The primary hypotheses for HR, are as follows:

Adults

$H_0: \mu = 3.25$

vs.

$H_A: \mu < 3.25$,

The primary hypotheses for RR, are as follows:

Adults

$H_0: \mu = 2.25$

vs.

$H_A: \mu < 2.25$,

where μ represents the population mean HR or RR.

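### No prospective rule lets the Monitor Device tester flag a displayed but unreliable gold-standard reading, so such a value counts as a valid pair and enters RMSD as device error

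*Combined protocol and SAP*

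**What the plan says.** Section 6.3 uses the same scheme in both accuracy tests. Two testers each record HR, RR and time from their own device at one-minute intervals.

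- **Who marks a failure.** In the Reference Device test (step 9), "the Reference Device tester will mark it on the CRF". In the Investigational Device test (step 10), "the Investigational Device tester will mark it on the CRF".
- **What triggers a mark.** In the RHEA test the trigger reads "If HR or RR value does not appear or turns darker and with a mark", followed by a question mark on the screen. In the EarlySense test it is a missing or blurred value. Apart from a missing value, these are display states of the under-mattress devices. No failure state of the monitor is named.
- **What a mark does.** Step 11 of the RHEA test says: "If certain values are marked (per Step 10 above), the data at that recorded point will not be considered in the analysis". Step 10 of the EarlySense test does the same by reference to its own step 9.
- **Who can see what.** The main units stand in different places "such that they can only be viewed by their respective testers".
- **When recording stops.** "Stop the test once 20 valid pairs of data are recorded for each subject".

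Section 10.2 defines RMSD from Y_R and Y_G, which "are the paired values for the RHEA Vital Sign Vigilance System and the gold standard method (Patient Monitor), respectively". It adds one further exclusion: "If motion or a bed exit occurs within 20 seconds preceding the recording period for a given data pair", the pair is not used. Sections 10.3 and 10.4 add no validity rule for the monitor value, and Section 10.4 computes the EarlySense RMSD in the same manner.

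**The concern.** The protocol accepts that a number on a screen is not always a current measurement, but it acts on this for one side of the pair only. If the monitor shows an HR or RR that is wrong because a lead or the nasal cannula has shifted, or that carries a signal-quality message, the Monitor Device tester simply writes it down. The other tester cannot see it. The pair counts as valid, and the whole difference is charged to the device under test.

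Two things are at stake. Followed as written, the rule tends to push RMSD up and widen its spread. That works against RHEA on both primary tests. It also adds noise to the paired comparison with EarlySense, because the two devices are tested at different times and would meet different bad monitor readings. Secondly, if someone later queries odd monitor values, no mark made at the time exists to rely on, and the plan sets neither a criterion nor blinding to the paired value. Removal driven by the size of the difference is then possible, and it would lower RMSD.

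**Working it through.** **Inputs from the documents.** Thresholds are 3.25 (HR) and 2.25 (RR) (Section 10.2). Success means that the upper limit of the two-sided 95% t interval lies below the threshold (Section 10.3), which is a one-sided 0.025 test. Planning means are 3.0 and 2.0, the SD of subject RMSDs is 0.75, n = 73, and the stated power is 80% (Section 10.6). There are 20 pairs per subject (Section 10.2). The pilot mean RMSD was 1.9 for HR and RR (Section 2.1).

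**Assumed, because the documents give nothing:** the share p of subjects with one bad monitor reading, and its error e.

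**Step 1: the plan's own figure.** One-sample t test, difference 0.25, SD 0.75, n = 73, noncentral t: power 80.2%. The stated 80% is reproduced.

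**Step 2: effect on one subject.** With 19 pairs at RMSD m and one pair with error e:

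RMSD = sqrt((19m² + e²)/20)

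- RR, m = 2.0: e = 6 gives sqrt((76 + 36)/20) = 2.37; e = 8 gives sqrt((76 + 64)/20) = 2.65; e = 10 gives sqrt((76 + 100)/20) = 2.97.
- HR, m = 3.0: e = 15 gives sqrt((171 + 225)/20) = 4.45.
- Single error that uses up the whole 0.25 margin for that subject: RR sqrt(20 × 2.25² − 19 × 2.0²) = 5.0 breaths/min; HR sqrt(20 × 3.25² − 19 × 3.0²) = 6.3 bpm.

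**Step 3: effect on power.** Let d be the rise in an affected subject's RMSD. The mean shifts by p·d, the SD becomes sqrt(0.75² + p(1−p)d²), and the distance to the threshold becomes (threshold − m) − p·d.

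Example: RR, m = 2.0, e = 10, p = 0.10. d = 2.966 − 2.0 = 0.966; distance 0.25 − 0.097 = 0.153; SD sqrt(0.5625 + 0.09 × 0.966²) = 0.804; power 36%.

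| Endpoint, true mean | p | Error e | Power at n = 73 |
|---|---|---|---|
| RR, 2.0 (planning) | 10% | 6 / 8 / 10 | 66% / 52% / 36% |
| RR, 2.0 (planning) | 5% | 6 / 8 / 10 | 74% / 67% / 59% |
| RR, 1.9 (pilot) | 10% | 6 / 8 / 10 | 93% / 87% / 74% |
| HR, 3.0 (planning) | 10% | 15 | 17% |
| HR, 1.9 (pilot) | 10% | 15 | over 99% |

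A simulation with gamma-distributed subject RMSDs (20,000 runs per scenario) gives 52% and 37% for RR at the planning mean with p = 10% and e = 8 and 10, and 18% for HR with e = 15. The closed form is adequate.

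**Step 4: does another rule catch the problem?** The Section 10.2 exclusion concerns motion or bed exit in the preceding 20 seconds, and the waiting times in Section 6.3 concern movement. Neither addresses a monitor fault in a still patient. Data queries (Section 9.2) and source verification and on-site checks (Section 11.3) exist, but they give no criterion for monitor values.

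**The case against.** The best case on the other side has four parts.

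1. **The gap is narrower than it first appears.** A reader might infer that only the device tester's mark can remove a pair; the motion and bed-exit exclusion in Section 10.2 contradicts that. A reader might infer that every monitor failure becomes device error; a blank monitor reading supplies no Y_G, so no difference exists and the pair is missing. A reader might infer that the monitor holds stale values; the documents describe held values only for the two under-mattress devices. And a reader might infer that bad values could later be removed only by looking at the discrepancy; Sections 9.2 and 11.3 provide query and verification routes, and a monitor value can be queried without its partner. All four limits stand. What remains is the displayed but unreliable value, with no rule for flagging it.

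2. **The setting makes bad readings less likely.** Subjects lie still, the lead is placed according to the monitor's instructions, and patients who cannot accept a cannula or chest lead are excluded. This is fair, but it supplies no rate.

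3. **The power figures may overstate the loss.** The pilot SD of 0.75 was itself measured against the reference method, and Section 2.1 says the pilot used the same testing procedure, so some reference error may already be in it. At the pilot mean of 1.9 the loss is far smaller. Both points stand. Against them, the pilot subjects were healthy volunteers and the trial enrols hospitalized patients, so the pilot need not cover ward conditions. Nor does one bad reading always dominate a subject's RMSD: at m = 2.0, errors of 6, 8 and 10 supply 36/112 = 32%, 64/140 = 46% and 100/176 = 57% of the sum of squares.

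4. **The bias is conservative.** As written, the gap raises RMSD and does not manufacture an accuracy claim. This stands for the primary tests. The opposite bias needs cleaning that the plan does not prescribe but also does not guard against.

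**Conclusion.** The concern holds in limited form. In both accuracy tests, a displayed but unreliable monitor HR or RR has no prospective route to being flagged, counts among the 20 valid pairs and enters RMSD as device error. The as-written consequence is an upward bias in RMSD, against RHEA, with lost power of unknown size and extra noise in the RHEA-EarlySense comparison.

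The power figures are illustrations. They rest on an assumed frequency and size of bad readings, on an SD that may already contain some of this error, and above all on the true mean: with 10% of subjects affected, RR power runs from 66% down to 36% at a mean of 2.0 but only from 93% down to 74% at 1.9, and the HR example runs from 17% at 3.0 to over 99% at 1.9.

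A reader might go further and conclude that the plan builds in outcome-driven cleaning in RHEA's favour. The documents do not support that: such removal is possible, because later queries have no criterion and no blinding to the paired value, but it is not the stated route. The gap still deserves correction before enrolment, because flags made at the time of reading cannot be recreated afterwards.

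**What to change.** Make the marking steps of Section 6.3 symmetric in both accuracy tests.

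- At each minute the Monitor Device tester, who cannot see the other display, marks on the CRF any HR or RR that is absent, accompanied by a technical or signal-quality message, or taken with a displaced lead or cannula.
- A mark by either tester voids the pair, and it does not count toward the 20.
- Section 10.2 states the same rule, and that no pair is excluded for monitor failure unless it was marked at the time.
- The report gives the number of excluded pairs by tester and reason, for each device.

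The cost is one CRF tick-box, a sentence in each section, and a few extra minutes of recording for some subjects. The Monitor Device tester is already present and recording every minute. The sample size does not change.

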10.4. Secondary Analyses

Accuracy of the RHEA will be compared with that of the Reference Device-EarlySense device. The RMSD for the Reference Device will be calculated for each subject in the same manner as described for the RHEA. Mean accuracy will then be compared between the RHEA and the Reference Device by comparing the individual subject RMSDs by a paired t test at the 5% level of significance.

Bland Altman plots will be presented separately for each subject's raw data, including the limits of agreement, for both the RHEA and the Reference Device methods. In addition, Bland Altman plots will be presented for the set of RMSD estimates across all subjects, along with two-sided

95% confidence intervals for their limits of agreement. Finally, Bland Altman plots of the raw data across all subjects will be presented, along with two-sided 95% confidence intervals for their limits of agreement. Methods discussed in Bland, JM and Altman, DG (4) and (5) will be used to calculate the confidence intervals of the limits of agreement due to the lack of independence of the repeated measurements on the same subject.

Motion and no motion accuracy will each be calculated along with their respective two-sided 95% confidence intervals. Motion accuracy will be calculated as the proportion of times that the device correctly detected motion among all actual occurrences of motion detected manually. Non-motion accuracy will be calculated as the proportion of times that the device correctly did not detect motion among all actual occurrences of no motion detected manually.

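### The motion and bed exit test crowds 13 prompted events into five minutes, leaves returns to bed untimed and sets no matching rule, so motion accuracy can be biased upward by notifications from neighbouring movements

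*Combined protocol and SAP*

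**What the plan says.** Section 6.3 (Motion and Bed Exit Test) has the Monitor Device tester "ask the subject to turn or move ten times and exit the bed for three times randomly in five minutes". The same tester keeps the reference log: "The Monitor Device tester will record the time of these events on the CRF". Those events are the turns or moves and the exits; getting back into bed is not listed. A second tester "will observe if there is an “unexpected motion” or “bed exit” notification on the screen of the Investigational Device" and notes the time.

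Section 10.1 refers to a time-stamp method for comparisons but states no tolerance. Section 10.4 gives the estimate: "Motion accuracy will be calculated as the proportion of times that the device correctly detected motion among all actual occurrences of motion detected manually". Its companion, non-motion accuracy, is taken "among all actual occurrences of no motion detected manually". Both get two-sided 95% confidence intervals.

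Neither section gives a minimum gap between prompts, a window within which a notification counts as a detection, a rule for a notification that could serve two events, or the unit of a no-motion occurrence.

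**The concern.** Motion accuracy is a sensitivity: of the movements that happened, how many did the device detect? That requires each notification to be tied to the movement that caused it. When movements follow each other within seconds and the matching rule is open, a turn the device missed can pick up the notification set off by the next turn, or by the subject climbing back into bed. The error runs mainly one way, since misses become hits, so the estimate is biased upward.

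Crowding also thins out the time that is clearly free of movement, which non-motion accuracy needs. Section 3 presents this third test as the assessment of motion and bed-exit detection, and no other test in the plan covers those functions. A matching rule chosen after the logs exist would also move the result.

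**Working it through.** **The plan's own figure.** The only derived figure in the plan is the sample size for the primary hypotheses. It reproduces: difference 0.25, SD 0.75 and two-sided 5% give 73 subjects with 80.2% power, and 73/0.95 = 76.8, hence 77. It does not bear on this point; the motion test has no sample size, target or success criterion.

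**Inputs from section 6.3.** Ten turns or moves plus three exits = 13 events; 5 min = 300 s; times random; three returns implied but not timed.

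**Assumptions (not in the documents).** Matching window w of 10 s or 30 s after each event; notification latency 0 to 5 s; true sensitivity s = 70%; each return triggers a motion notification with the same 70% chance; returns fall at random times; exits give only a bed-exit notification; motion accuracy is scored on the ten turns; one notification may be credited to more than one turn.

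**1. Spacing.** Mean 300/13 = 23.1 s. For 13 random times, P(gap < 10 s) = 1 − (1 − 10/300)^13 = 0.356; P(gap < 20 s) = 1 − (1 − 20/300)^13 = 0.592.

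**2. Carry-over.** A missed turn is wrongly credited if a notification from any of the other 9 turns or 3 returns falls in its window. Each does so with probability about s·w/300, ignoring edge effects. Hence

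apparent accuracy ≈ s + (1 − s)·[1 − (1 − s·w/300)^12].

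- w = 10 s: s·w/300 = 0.0233; 1 − 0.9767^12 = 0.247; 0.70 + 0.30 × 0.247 = 0.774.
- w = 30 s: s·w/300 = 0.07; 1 − 0.93^12 = 0.581; 0.70 + 0.30 × 0.581 = 0.874.
- If returns trigger nothing (exponent 9): 0.70 + 0.30 × 0.191 = 0.757 and 0.70 + 0.30 × 0.480 = 0.844.
- If s = 90%: 0.90 + 0.10 × (1 − 0.97^12) = 0.931 and 0.90 + 0.10 × (1 − 0.91^12) = 0.968.

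**3. Effect of a one-to-one rule.** If each notification is used once and returns trigger nothing, expected credits cannot exceed 10 × 0.70 = 7 of 10, so the average is not inflated. If returns do trigger notifications, a further 3 × 0.70 = 2.1 are available, a ceiling of 9.1 of 10. The rule therefore removes re-use but not the contribution of untimed returns.

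**4. Events 60 s apart.** With latency of at most 5 s and a window of 10 s or 30 s, no notification from another prompted event falls in a turn's window. If the subject is back in bed and any resulting notification has appeared before the next prompt, the score is about 70%, the true value.

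**5. No-motion time.** The expected share of the five minutes lying outside a window of w seconds after each event is about (1 − w/300)^13. For w = 10 s this is 64%, and for w = 30 s it is 0.9^13 = 25%. Counting the three returns (exponent 16), the shares are 58% and 19%.

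**The case against.** The strongest case against is that most of this can be repaired in the analysis. Two testers record times, the two notification types are distinct, and the accuracy-test procedure synchronises the device clocks. A short window with one-to-one crediting would attribute many events correctly, and non-motion accuracy is reported alongside to expose over-firing. Much of that stands. What remains is that the window, the one-to-one rule and the no-motion unit are not written down, and that no analysis rule recovers returns that were never timed or clearly separates movements a few seconds apart.

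Three stronger readings are tempting, and the documents do not support them.

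- A reader might set the 23.1 s spacing against the stable time in section 6.3: "Thirty seconds is considered to be reasonable for Investigational Device and 1 min for Reference Device". That wait applies to rate readings: "Make sure there is sufficient stable time before the HR and RR results are recorded for the Investigational Device and Reference Device". The 20 s rule in section 10.2 likewise only excludes heart rate and respiratory rate pairs. Neither is a latency or reset time for notifications, and the plan gives none.
- A reader might infer that notifications cannot be attributed at all. With recorded times and a tight window, many can.
- A reader might infer that crowding lets a randomly firing device score well, and that spacing cures it. With re-use allowed, chance credit depends on firing rate and window, not on spacing. Thirteen random notifications in 300 s with a 10 s window give 1 − (1 − 10/300)^13 = 0.356. At the same rate over 780 s (about 34 notifications) the result is 1 − (1 − 10/780)^34 = 0.355. Spacing helps against carry-over between real movements, which is a different mechanism.

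**Conclusion.** The concern holds as a bias in a secondary estimate. Crowded prompts, untimed returns and an open matching rule let notifications from one movement be credited to another, which pushes motion accuracy upward and leaves little clear no-motion time.

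Under the stated assumptions, a true 70% would appear as about 77% (10 s window) to 87% (30 s window). The gain is about 3 to 7 points if true sensitivity is 90%, and less under one-to-one crediting. These figures illustrate the mechanism and are not predictions: latency, window, sensitivity and the effect of returns are all assumed, because the documents settle none of them.

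Motion accuracy has no hypothesis or success criterion, and the primary heart rate and respiratory rate conclusions do not depend on it. The change is worth making because it is cheap and because this is the plan's only test of these functions.

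**What to change.** In section 6.3, keep the ten movements and three exits but prompt them in random order with a minimum gap longer than the matching window, for example about 60 s apart. Time each return to bed as its own event, completed before the next prompt.

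In section 10.4, pre-specify:

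- a matching window based on the device's own notification latency, from bench or pilot data, since a window shorter than the latency would score true detections as misses;
- that each notification is credited to one event only;
- whether exits and returns count as motion;
- the no-motion unit, for example the quiet intervals between windows.

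Cost: 13 × 60 s = 780 s, or 13 minutes instead of 5, so about eight more minutes for subjects who do this test. That should fit the one-to-two-hour session stated in section 3. It needs a revised CRF schedule and a short addition to section 10.4, with no extra staff.
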